The audio component of the mindfulness intervention featured a female narrator guiding participants through mindfulness exercises, focusing on breath awareness and cultivating non-judgmental attention to thoughts and feelings. Ambient tonal sounds, including a harmonic drone with slow timbral changes, played softly in the background to support relaxation. Importantly, no rhythmic audio cues were included to avoid inducing breathing entrainment. This setup emphasized passive, mindful observation rather than active breath control, encouraging participants to observe their bodily sensations and thoughts without judgment.

Measures

Demographics. Participant age and gender were collected from families as part of the student's involvement in the after-school program.

Revised Children's Manifest Anxiety Scale (RCMAS). To measure the level and nature of anxiety symptoms, the RCMAS Arabic version was administered to participants via a web-based survey. The RCMAS is a self-report questionnaire that lists feelings or actions and was administered to all participants pre- and post-intervention. Participants answer "yes" if that item is generally descriptive of their own feelings or actions, or "no" if not. The RCMAS produces a total anxiety score based on 28 items, with three subscales: physiological anxiety,

worry/oversensitivity, and social concerns/concentration. Higher scores represent more anxiety symptoms. Both the English and Arabic versions of the RCMAS have been shown to have acceptable reliability and validity in school-aged children. Similar to previous studies using the RCMAS, if at least 80% of items for each scale was present, missing data was imputed using the within-subject mean of the non-missing items in the same scale. In the current sample, the total score showed good internal consistency ($\alpha = .82$).

The Self-Efficacy Questionnaire for Children (SEQ-C).

The Self-Efficacy Questionnaire for Children (SEQ-C) measures three types of self-efficacy: (1) social self-efficacy, measuring children's capability to deal with social challenges; (2) academic self-efficacy, measuring children's perceived capability to master academic affairs; and (3) self-regulatory efficacy, measuring children's ability to resist peer pressure to engage in high risk activities.

Translated PHQ-9

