A validated measure of depressive symptoms, consisting of nine items assessing the frequency of depressive symptoms over the past two weeks. The PHQ-9 has demonstrated strong psychometric properties, including reliability and validity in clinical and non-clinical populations, including the translated Arabic version.

Data Analysis

Analyses were conducted using R. Group differences at baseline in anxiety, depression, and self-efficacy scores were examined using ANCOVAs and post hoc Tukey pairwise tests. For the primary analyses, four analyses of covariance (ANCOVAs) were conducted. For each ANCOVA, the independent variables were condition (paced breathing or mindfulness intervention vs. control) and time of observation (before or after the intervention), the dependent

variable was the behavioral scale (RCMAS, SEQ-C, PHQ-9) at post-intervention, and the covariate was gender. Exploratory general linear models (GLMs) were conducted to examine whether gender moderated the relationship between condition and anxiety or depression symptoms. For significant GLMs, post-hoc GLMs were conducted to examine the relationship between condition and anxiety or depression symptoms within each subgroup. All tests were two-tailed, no test assumptions were violated, and findings were considered significant at $p < .05$.

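### Four primary ANCOVAs are declared for three named scales, each tested at .05 without a multiplicity rule, and the model contradicts itself, so no test is identified as deciding for paced breathing

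*Combined protocol and SAP*

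**What the plan says.** All the analysis text is in the Data Analysis section of the combined protocol and SAP.

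- **Number of primary tests:** "For the primary analyses, four analyses of covariance (ANCOVAs) were conducted".
- **Factors:** "condition (paced breathing or mindfulness intervention vs. control") and "time of observation (before or after the intervention").
- **Outcome:** the dependent "variable was the behavioral scale (RCMAS, SEQ-C, PHQ-9) at post-intervention". Gender is the only covariate named.
- **Error control:** "All tests were two-tailed, no test assumptions were violated, and findings were considered significant at" p < .05. The one multiple-comparison procedure named belongs to another question: "Group differences at baseline in anxiety, depression, and self-efficacy scores were examined using ANCOVAs and post hoc Tukey pairwise tests".

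The Measures section shows which scores could be analysed. The SEQ-C "measures three types of self-efficacy". For anxiety, "The RCMAS produces a total anxiety score based on 28 items, with three subscales: physiological anxiety" and two others. The PHQ-9 is described as a single nine-item measure.

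The Procedure section gives three conditions (paced, mindfulness, control) of near equal size, with assignment stratified by age and gender. The intervention section says that the school teacher ran sessions in groups of about ten. The title attributes a mental-health benefit to paced breathing specifically.

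**The concern.** A reader cannot tell from the plan which result would establish the title's claim. Three things are open.

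1. **Which outcomes are primary.** The stated count does not match the list of scales.
2. **How many must succeed.** Each test is judged alone at .05. No rule says whether one significant scale is enough.
3. **Which term decides.** With three arms, the condition wording fits a pooled active-versus-control contrast, a three-level omnibus test, or each active arm against control. The first two do not by themselves isolate paced breathing. In addition, a post-only outcome has no before level, so a before/after factor cannot be fitted to it. The model cannot be run as written.

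At stake is whether a single headline claim rests on one of several unadjusted tests, or on a term that is not the paced-breathing effect.

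**Working it through.** **1. Can the count of four be reproduced?** From the scores in Measures:
- one score per scale: 1 + 1 + 1 = 3;
- SEQ-C by its three types: 1 + 3 + 1 = 5;
- RCMAS by subscales in place of the total, and SEQ-C by type: 3 + 3 + 1 = 7.

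None of these gives four. RCMAS total plus three subscales is four, but for RCMAS alone. Measures reports internal consistency for the RCMAS total, so the subscale option is the least likely. The fourth analysis remains unidentified.

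**2. Does the sample-size statement reveal the deciding test?** Inputs from Participants: f = .25, 90% power, N = 130. A three-group one-way test at .05 needs 207 in balanced groups. A two-group between-factor test on two measurements with correlation .5 has noncentrality N·f²·m/(1+(m−1)ρ) = 130 × .0625 × 2/1.5 = 10.83 and power 90.4%, so 130 fits. That would suit a pooled active-versus-control comparison. The group number, the measurement number and the correlation are all unstated, so this is a hint and no more.

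**3. Chance of at least one false primary result.** Assumptions: all nulls true, one condition test per outcome with a true 5% error rate, no clustering.
- Independent outcomes, 1 − .95^k: k = 3 gives .1426; k = 4 gives .1855.
- Correlated outcomes: null simulation of the three-arm omnibus test, 71 per arm (213/3, assuming equal arms). At an assumed correlation of .9 it gives about 8.5% (three) and 9.5% (four).
- If each active arm is read against control on every outcome: about 25% and 32% at zero correlation, 15% and 16.5% at .9.

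**4. Sensitivity to the model reading.** Step 3 requires a valid 5% test. Suppose instead that before and after rows were fitted together with no subject term. The per-test rejection rate is then P(F(2,420) > Fcrit/(1+ρ)) for the condition main effect and P(F(2,420) > Fcrit/(1−ρ)) for condition-by-time, where ρ is the pre-post correlation. At an assumed ρ = .5 these are .135 and .0026. Over four independent outcomes, 1 − (1−.135)^4 = .44 and 1 − (1−.0026)^4 = .010. The same data could therefore give an error rate far above or far below 5%, depending on an unstated choice.

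**5. Power under Holm.** Illustration for paced versus control: assumed d = .5, 71 per arm, no clustering or dropout. Noncentrality is .5 × √(71/2) = 2.98.

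| Level | Post-only | Baseline-adjusted, assumed ρ = .5 |
|---|---|---|
| .05 | 84% | 93% |
| .05/3 = .0167 | 71% | 84% |
| .05/4 = .0125 | 67% | 82% |

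The adjusted column divides d by √(1 − .5²), giving .577 and noncentrality 3.44.

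**6. Does Holm alone hold 5%?** Not if the groups are ignored. Take groups of ten in the paced arm, unclustered controls and three independent outcomes. The variance of the difference is multiplied by (1 + 9·ICC + 1)/2 = 1 + 4.5·ICC. The chance of any Holm rejection is 1 − (1−p)³ with p = P(|Z| > 2.394/√(1 + 4.5·ICC)). This is about 6% at an assumed ICC of .01, 9% at .05 and 13% at .10.

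**The case against.** Several objections carry weight. The count of four may be a one-word slip. Anxiety, depression and self-efficacy are distinct constructs, and separate claims per scale need not share one error budget; the plan never says that any one scale suffices. The gender analyses are already labelled exploratory. In so short a document, an unmentioned subject term may simply have been left out. The value d = .5 matches f = .25 only for two equal groups, so the power figures are illustrative.

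These points limit the claim but do not remove it. A slip still needs correcting, because the number of outcomes sets the size of the family. Separate claims per scale would be defensible if the plan said so, but it calls all four analyses primary and gives no rule for combining them.

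Two stronger readings are tempting. One is that the false-positive rate is known to be inflated, perhaps to the 44% in step 4. The documents do not support this: they do not say that rows were treated as independent, or that a main effect averaged over before and after was read as the treatment effect. The other is that the results are false or that an outcome was concealed. Nothing in the text shows either.

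**Conclusion.** The point holds and should be addressed. The primary outcomes are miscounted, no rule controls error across them, and the stated model is internally inconsistent, so the deciding test for paced breathing is not defined.

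The multiplicity figures (about 14% or 19% with independent outcomes, 8.5% to 9.5% at a correlation of .9) depend on all nulls being true and each test having an exact 5% error rate. The documents give no outcome correlation, pre-post correlation or arm sizes; those used here are assumptions. Outside those conditions neither the direction nor the size of the error can be established from the documents. Confidence is medium for that reason; the textual contradictions themselves do not depend on any assumption.

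**What to change.** 1. Correct the count of four or name the fourth outcome, and state which SEQ-C and RCMAS scores are used.
2. For each declared primary scale, regress the post-intervention score on three-level condition, that scale's baseline score, gender and age, with an error term that allows for the teacher-led groups of about ten. Age belongs in the model because assignment was stratified on it.
3. Take the adjusted paced-versus-control difference as the deciding test.
4. Apply Holm across the declared primary scales. Report mindfulness versus control and paced versus mindfulness as supporting, or add them to the Holm family if they are claimed.
5. The text describes completed analyses, so label any outcome, contrast or model term chosen now as post hoc unless earlier documentation supports it.

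The order matters: Holm cannot repair a term whose own error rate is wrong.

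**Cost.** SAP wording and reanalysis of data already held. Power at the strictest Holm step is lower, as tabulated above, and baseline adjustment recovers part of the loss. Adding mindfulness versus control would lower the post-only figure further, to 62% (six tests) or 58% (eight tests). Holm relaxes the level at later steps. Allowing for the groups will reduce power by an amount that the documents do not let one compute.

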Musically-Guided Paced Breathing Improves Mental Health in War-Affected Adolescents

Study Protocol and Statistical Analysis Plan

NCI Number: NCT06988800

January 21, 2024

Participants

Students were included in this study if they were children aged 13-17 years and enrolled at a school in a war-torn area in the West Bank in the Middle East. Students were excluded if they had a known diagnosis that may have impeded their participation (e.g., epilepsy, substance abuse, attention-deficit/hyperactivity disorder). In order to have 90% power to detect a medium effect size ($f = .25$), 130 participants would be required, and the total number enrolled was 213. Consent forms stated that the goal of the intervention was to reduce anxiety and manage stress. The study protocol was approved by an Institutional Review Board that consisted of two independent researchers in the study region.

Procedure

Participants were randomly assigned, stratified by age and gender, to an intervention or control condition. After all consents were collected, an individual external to the study team divided participants into near equal groups based on age and gender, which were then used to assign participants to one of the three conditions. Only the individual who randomized the participants and the group facilitators were provided access to the document linking the name and de-identified participant identifier.

Participants in the control condition completed other typical after-school activities while participants in the intervention condition completed one of two breathing interventions: paced breathing (paced), or mindful breathing (mindfulness). Participants in the control condition were given the opportunity to complete the intervention after the study ended. All participants in the intervention and control conditions completed a pre-intervention measure of anxiety, depression, and self-efficacy. Participants in the intervention condition then completed 12 sessions of the guided paced breathing audiovisual intervention, held 2 times a week for 5 weeks. After the 4th

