week of the intervention, all participants in both the intervention and control conditions completed a mid-intervention measure of anxiety, depression, and self-efficacy. The study was then paused for one month during Ramadan, and resumed at the beginning of the following month. After the 5th total week of the intervention, all participants in both the intervention and control conditions completed a post-intervention measure of anxiety, depression, and self-efficacy.

Guided Paced Breathing Audiovisual Intervention

Each intervention session was conducted by the school teacher, who guided groups of approximately ten participants in classrooms. The groups were separated by gender and age (e.g., 16-year-old boys). Participants were seated comfortably with a clear view of a screen displaying the audiovisual intervention, and the audio was played at a comfortable volume. Each session began with an educational introduction, which outlined the benefits of paced breathing, such as how it can positively impact well-being and mental health (e.g., "A strong sense of well-being helps you to feel good about yourself and the way your life is going, which can have a hugely positive impact on your mental health").

Following the introduction, the intervention transitioned into a three-minute audiovisual guided paced breathing exercise. The paced breathing condition used timed auditory and visual cues to guide participants through breathing cycles at a rate of five breaths per minute, designed to stimulate the parasympathetic nervous system and promote relaxation. The audiovisual cues included spoken instructions, music, and breath-like sounds. The tonal audio cues rose in pitch during inhalation and fell during exhalation, creating a clear auditory signal for breath pacing. The same harmonic drone used in the mindfulness intervention provided a calming background, though here it was combined with the rhythmic pacing. Visually, the pacing was synchronized

with the image of a lotus flower opening during inhalation and closing during exhalation, reinforcing the breathing rhythm.

Mindfulness Intervention

The mindfulness intervention employed a similar visual setting, featuring the same lotus flower graphic. However, instead of rhythmic pacing, the lotus flower remained open at the start of the session and gradually closed over the course of the 3 minute exercise. This visual served as a symbolic anchor for the participant's growing awareness and focus.

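### The primary ANCOVA lists time (before/after) as a factor but fixes the outcome at post-intervention, so it cannot be fitted as written and the treatment test is undefined

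*Combined protocol and SAP*

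**What the plan says.** The Data Analysis section is the only analysis text. It announces four primary ANCOVAs and describes them in one sentence. In each, "the independent variables were condition (paced breathing or mindfulness intervention vs. control) and time of observation (before or after the intervention"). The sentence then says that the dependent "variable was the behavioral scale (RCMAS, SEQ-C, PHQ-9) at post-intervention, and the covariate was gender".

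The section names no condition-by-time term, no participant term, no repeated-measures or mixed model, and no baseline score as covariate.

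Three statements elsewhere bear on the point:

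- **Baseline scores exist.** The Procedure section says: "All participants in the intervention and control conditions completed a pre-intervention measure of anxiety, depression, and self-efficacy".
- **Randomisation was stratified.** The same section says: "Participants were randomly assigned, stratified by age and gender".
- **Sample size.** For 90% power at f = .25, the Participants section says "130 participants would be required, and the total number enrolled was 213".

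**The concern.** A post-intervention outcome has no before rows. Time is therefore a constant, identical to the intercept, and the sentence lists a factor that its own outcome definition removes. Whoever runs the analysis must replace this model with another, and the plan does not say which.

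The candidates differ in three ways:

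- **Estimand:** the post-intervention difference, the average of the pre and post differences, or the difference in change.
- **Error term:** between participants, within participants, or a pooled residual that treats a participant's two scores as unrelated.
- **Power.**

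This sentence governs every primary result. A reader cannot tell which analysis a reported p-value comes from, and the plan does not prevent the choice being made with the data in view.

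**Working it through.** **1. Can the model be fitted?** Take one row per participant (N = 213), with columns for intercept, two condition indicators, time and gender. That is 5 columns of rank 4, because time equals the intercept. Adding condition-by-time gives 7 columns, still of rank 4. Software will either reject the one-level factor or drop it, which leaves post score on condition and gender.

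**2. Does the sample size reveal the intended model?** Inputs are f = .25 and 90% power (Participants) and two-tailed alpha .05 (Data Analysis). I use the noncentral F with λ = N × f² × m, where m depends on the model. At N = 130, N × f² = 130 × 0.0625 = 8.125.

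| Model | m | λ at N = 130 | Power | N for 90%, equal groups |
|---|---|---|---|---|
| Two groups, post only | 1 | 8.125 | 0.808 | 172 |
| Three groups, post only | 1 | 8.125 | 0.714 | 207 |
| Two groups, two measurements, between-participant test, ρ = 0.5 | 2/(1 + 0.5) = 1.333 | 10.83 | 0.904 | 130 |
| Two groups, baseline-adjusted, ρ = 0.5 | 1/(1 − 0.25) = 1.333 | 10.83 | 0.904 | 130 |

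The stated 130 is reproduced, but only with two groups and an assumed correlation of 0.5, and then by two different models equally well. It does not identify the primary model. The post-only wording does not reproduce it.

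**3. How much does the choice matter?** These assumptions are not in the documents: 213/3 = 71 per arm, unit-variance scores, pre-post correlation ρ of 0.4 to 0.7, independent participants (classroom groups ignored), and a 0.5 SD post-intervention effect in the paced arm only.

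*Type I error with rows stacked as independent.* The variance of the condition main effect is really (1 + ρ) times what the model assumes; for condition-by-time it is (1 − ρ) times. A 2-df test at the 5% critical value 5.991 therefore rejects with probability exp(−5.991/(2(1 ± ρ))).

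| ρ | Condition main effect, 2 df | Condition-by-time, 2 df |
|---|---|---|
| 0.3 | 10.0% | 1.4% |
| 0.4 | 11.8% | 0.7% |
| 0.5 | 13.6% | 0.25% |
| 0.6 | 15.4% | 0.06% |
| 0.7 | 17.2% | 0.005% |

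For a 1-df contrast the main effect gives 2(1 − Φ(1.96/√(1 + ρ))), which is 9.8% to 13.3% for ρ of 0.4 to 0.7. Simulation with 20,000 replicates agrees: 11.8% to 17.2% for the 2-df main effect, and 0.8% falling to 0.0% for the 2-df interaction.

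*Estimate.* The pre rows carry no treatment effect, so a condition main effect over both times estimates (0 + 0.5)/2 = 0.25 SD. Condition-by-time keeps the full 0.50 SD.

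*Power of the versions that hold 5%.* With arm means (0.5, 0, 0), the variance of the means is 0.25/3 − (0.5/3)² = 0.0556, so λ = 213 × 0.0556 = 11.83 for the post-only test. The other versions rescale this λ.

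| Model | λ | ρ = 0.4 | 0.5 | 0.6 | 0.7 |
|---|---|---|---|---|---|
| Participant term, condition main effect | 11.83/(2(1 + ρ)) | 0.431 | 0.405 | 0.383 | 0.362 |
| Post only, time dropped | 11.83 | 0.87 | 0.87 | 0.87 | 0.87 |
| Participant term, condition-by-time | 11.83/(2(1 − ρ)) | 0.804 | 0.874 | 0.938 | 0.983 |
| Post adjusted for pre | 11.83/(1 − ρ²) | 0.926 | 0.951 | 0.976 | 0.993 |

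Simulated null rejection for these four was 4.8% to 5.3%. The stacked condition-by-time test, though very conservative, had simulated power of about 52% to 56%. No power is given for the stacked main effect because its size is inflated.

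**The case against.** The strongest reply is that this is loose drafting, not a broken analysis. If the outcome was meant to cover both measurements, a model can be fitted. If software drops time, the remaining post-only comparison of randomised arms is valid and has 87% power under the assumptions above. Nothing in the documents says that rows were stacked as independent, so the inflated error rate is hypothetical. The text is in the past tense, so some model had apparently already been chosen. Adjustment for baseline and age is good practice but not the only possible correction.

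Much of this is fair. The stacked-row figures show what one reading would do, not what was done. The unadjusted post-only model is valid. The sample-size check is only supporting evidence and settles nothing.

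The central point stands, however. If two rows per participant were meant, the tested term and error term are still missing. If time is dropped, the model is not the one described, and it leaves unused a baseline score taken from everyone. The past tense makes the gap a reporting problem as well, because a reader cannot tell which model produced the results.

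**Conclusion.** The concern holds and must be fixed. The stated primary model lists a term that cannot be estimated from its stated outcome, and nothing elsewhere in the document resolves this. That conclusion needs no assumption.

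The size of the consequence does depend on assumptions: equal arms, independent participants, and a pre-post correlation that the documents do not give. For correlations of 0.4 to 0.7, the readings run from a 2-df type I error of 17.2% down to almost zero. Among the tests that hold 5%, power runs from 36% to 99%. At a correlation of 0.3 the two stacked-row error rates are 10.0% and 1.4%, in the same directions.

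**What to change.** Delete time of observation from the primary ANCOVA. For each scale, use one row per participant and regress the post score on:

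- condition at three levels, with control as reference;
- the pre score of the same scale;
- the stratification factors, age and gender.

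Name the 2-df condition effect as the tested term, followed by each intervention arm against control. State the three levels explicitly, because the present wording could be read as pooled intervention against control. Also say what the fourth ANCOVA is, since only three scales are listed.

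If time is to stay, fit a repeated-measures or mixed model to the pre and post rows with a participant term, and define the treatment effect as the condition-by-time contrast at post-intervention. Add mid-intervention rows only for scales that have them. The Procedure section says that all participants "completed a mid-intervention measure of anxiety, depression, and self-efficacy", whereas the Measures section says that the RCMAS "was administered to all participants pre- and post-intervention". These two statements need reconciling first.

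The cost is a change of SAP wording and of the R model. Pre scores, age and gender were all collected, so no new data are needed. Because the analyses are described as done, the sponsor should state which model was run, re-run any analysis that treated stacked rows as independent, and disclose the change.

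### The gate for the within-gender models does not name the condition x gender term; one interaction model, reported whatever its p-value, would be better and costs almost nothing

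*Combined protocol and SAP*

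**What the plan says.** The Data Analysis section sets out the gender analysis in two steps. The first is a moderation question on two outcomes: "Exploratory general linear models (GLMs) were conducted to examine whether gender moderated the relationship between condition and anxiety or depression symptoms". The second is a conditional follow-up: "For significant GLMs, post-hoc GLMs were conducted to examine the relationship between condition and anxiety or depression symptoms within each subgroup". The closing sentence of the section applies one threshold to everything: "findings were considered significant at" the two-sided .05 level.

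The text leaves three things open:
- which term or test makes a GLM count as significant;
- whether the moderation estimate and its confidence interval are reported;
- how two within-gender results are to be compared.

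The follow-up is described as separate models by subgroup, not as contrasts taken from one model. The analyses are labelled exploratory.

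**The concern.** A model containing condition, gender and their product can be significant with no moderation at all. An overall difference between boys and girls, or an overall condition effect, is enough. If that opens the gate, the reader is shown two separate tests at .05, one per gender. When each has moderate power they will often disagree by chance. A pair of labels, one significant and one not, is not a test of whether the effects differ, which is the question the plan asks.

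Naming the interaction as the gate removes most of this problem but not all of it. Gender-specific estimates that are produced only after a significant interaction come from the trials in which the apparent difference happened to be large. At stake is how far a reported gender difference in effect can be trusted. The primary comparison is not affected.

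**Working it through.** **The plan's own figure.** The Participants section says that "130 participants would be required" for 90% power at f = .25. A two-group, two-time repeated-measures test of the between factor, with an assumed correlation of 0.5, has noncentrality N x f² x 2/(1 + 0.5). It needs N = 129, or 130 with equal groups. The two groups and the correlation are assumptions. A one-way comparison would need 171 (two groups) or 206 (three groups). The plan gives no power figure for a gender analysis, so the rest is new calculation.

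**Inputs.**
- Size: "the total number enrolled was 213" (Participants).
- Three conditions. The Procedure section says the external individual "divided participants into near equal groups based on age and gender, which were then used to assign participants to one of the three conditions", so equal arms are assumed: 213/3 = 71.
- Gender split: not stated. Assumed even, so 71/2 = 35.5 per gender per arm (36 and 35 in the simulations).
- Effect: f = .25 equals d = 2 x 0.25 = 0.5 for two equal groups. Effects of 0.2, 0.3 and 0.8 SD were also tried.
- Overall gender difference in symptoms: not stated. 0 and 0.4 SD were tried.
- Independent normal errors with SD 1, and no dropout.

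**Step 1: no gate, paced versus control.** Within one gender the SE of the difference is sqrt(2/35.5) = 0.237 SD. At d = 0.5 the standardised effect is 0.5/0.237 = 2.11 and power by noncentral t is 0.547. With the same true effect in both genders, the chance that exactly one is significant is 2p(1 - p) = 2 x 0.547 x 0.453 = 0.50. That is the ceiling of the formula when power is equal in both genders. At d = 0.2 it is 0.23 and at d = 0.8 it is 0.16.

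**Step 2: with the gate.** Trials were simulated (20,000 per scenario) with the same effect in both active conditions and both genders, and no interaction. The follow-up is the three-condition F test within each gender. The table gives the percentage of all trials in which the gate opens and exactly one gender is significant. Ranges run over a gender difference of 0 to 0.4 SD.

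| True effect (SD) | Gate = whole model | Gate = interaction |
|---|---|---|
| 0.2 | 12-21% | about 4% |
| 0.3 | 22-34% | about 4% |
| 0.5 | 41-49% | about 3% |
| 0.8 | 11% | 1-2% |

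At 0.5 SD with a 0.4 SD gender difference, the whole model is significant in 95% of trials and the interaction in 5%. The pattern of condition effects matters too: other planned-size patterns with no gender difference gave whole-model figures down to 28%. A gate on the condition main effect gives 36-47% for planned-size effects.

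Under the interaction gate, two outcomes open it falsely at most about 1 - 0.95² = 9.75% of the time if they are independent. Among false openings at planned-size effects, 66-79% show significance in one gender only.

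**Step 3: exaggeration after an interaction gate.** For the one-degree-of-freedom paced-versus-control contrast, the SE of the difference between genders is sqrt(2/36 + 2/35) = 0.336 SD. To reach p < .05 the estimate must exceed 1.96 x 0.336 = 0.66 SD in absolute size. A true difference of 0.3 SD passes about 15% of the time, and the passing estimates average 0.81 SD, or 0.81/0.3 = 2.7 times the truth. The factor falls to about 1.75 at a true 0.5 SD and 1.2 at 0.8 SD.

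**The case against.** The strongest reply is that the sentence just before the gate describes these GLMs as tests of moderation. A significant GLM then most naturally means a significant moderation result, and the follow-up is ordinary simple-effects work after an interaction. The whole-model F test is never mentioned. This largely stands, and it is why the interaction reading is treated as the likelier one.

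A reader might infer something stronger: that any significant GLM opens the subgroup step, so that an equal effect would be reported as working in one gender only about half the time, and the programme would then be offered to the wrong students. The documents do not support this. They do not say that any significant GLM suffices. About half needs both the whole-model reading and within-gender power near 50%. No rule for claiming a one-gender effect is stated, and nothing links gender results to who is offered the programme.

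Two further replies carry weight. With no condition effect and a 0.4 SD gender difference, the whole-model gate gives at least one false within-gender result in 8.6% of trials per outcome. That is no worse than two ordinary tests at .05 (9.75%), so it adds nothing to the case. The 2.7-fold figure applies to the interaction contrast at one chosen true value, and the plan does not say that a non-significant interaction estimate would be withheld.

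What remains is that the gating term is unnamed, the follow-up is by separate models each tested at .05, and the within-gender estimates exist only after a significant result.

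**Conclusion.** The point holds as a gap in specification with a better method at hand. One undefined term moves the rate of one-gender-only significance under equal effects from about 1-4% per outcome (interaction gate) to roughly 11-49% (whole-model gate; about 40-49% at 0.5 SD in both active conditions). Selection on significance exaggerates the reported gender difference even on the favourable reading, most of all when the true difference is small relative to its SE of 0.336 SD.

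These figures assume equal arms, an even gender split, a gender difference of 0-0.4 SD, complete data and independent observations. Sessions ran in gender-separated groups of about ten. Unmodelled clustering could therefore raise the interaction's false-positive rate above 5%, but no intraclass correlation is given and this is not quantified. Because the analyses are exploratory, the consequence is limited, and this is best classed as a cheap improvement.

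**What to change.** Replace the two-step rule with wording such as this: for RCMAS and PHQ-9, fit one model with condition, gender and condition x gender. The condition x gender term is the only test of moderation. Whatever its p-value, report from that model the gender-specific condition contrasts and the difference between them, with 95% confidence intervals. Separate within-gender significance tests are not used to claim moderation. The exploratory label stays.

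The cost is a few sentences in the plan and a few lines of R, with no new data. The one small downside is that a one-gender claim based on separate p-values is no longer available.
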